Use liver biopsy as “golden standard” for pathological staging, to evaluate the clinical values of FibroTouch for the non-invasive and quantitative diagnosis of liver fibrosis and cirrhosis in CHB patients.

(II) Secondary Objective

- ◆ Difference between FibroTouch and FibroScan in the rate of d successful detection
- ◆ Difference between FibroTouch and FibroScan in the determined values
- ◆ Correlation between determined values of FibroTouch and ultrasonic semi-quantitative scores
- ◆ Performance of FibroTouch.

- Positioning accuracy evaluated by investigators
- Image displaying ability evaluated by investigators
- Scanning speed evaluated by investigators
- Detecting and calculating speed evaluated by investigators

III. Study Goal

To determine the diagnostic accuracy, specificity and sensitivity of FibroTouch for liver fibrosis assessment in CHB patients.

IV. Study Type

It's a prospective and multicenter study.

V. Anticipated Total Cases

According to publications on FibroScan and liver biopsy examination, the mean sensitivity and specificity are 0.61 and 0.90 respectively for different stages (four pathological stages: $\geq F4$, $\geq F3$, $\geq F2$ and F0-F1). Assuming a similar sensitivity and specificity of FibroScan and FibroTouch, the lowest clinically acceptable sensitivity and specificity is 0.55

and 0.8 respectively, when $\alpha=0.05$ and power=80%, 423 cases are required based on sensitivity; total 529 cases are required based on the determination effectiveness=80%; 328 cases are required based on specificity; total 410 cases are required based on the determination effectiveness=80%. By considering the center assignment, ≥ 600 qualified cases are included to guarantee 500 final statistical cases; and ≥ 100 cases are required for S0+S1, S2, S3, S4 and liver cirrhosis (compensatory stage) respectively. For each stage, the case is assigned as equally as possible.

VI. Study Time

One year (from May 2014 to May 2015).

VII. Case Assignment System (via central registration system)

Subject No. is assigned through IWRS system. After the investigator logs in the system and fills in the pathological stages, this system will, according to the completed contents, automatically assign the sole subject No. for this subject.

VIII. Statistical Analysis

Peking University Clinical Research Institute

IX. Study Design

(I) Inclusion Criteria

1. Age: 18—65 years, both gender.
2. History of HBV or HBsAg positive > 6 months up to now.

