<2>. In order to determine accurately, image-guided positioning with ultrasonic B probe should be performed prior to the scanning with liver fibrosis probe. Apply ultrasonic coupling agent to the patient's skin at the position of right side, interspace between the Seventh and eighth rib along the midaxillary line, place the ultrasonic B probe perpendicularly on the skin, and then turn on the FibroTouch image-guided scanning model. Investigator can choose the proper position for liver examination with reference to the ultrasonic B image on the video display screen.

The testing position (at the center line of ultrasonic B image) is selected as following roles:

1. Be away from the heterogeneous liver tissues, such as great vessels, cysts and nodes.
2. Be away from the edge of liver.
3. The position where liver tissue are homogeneous, well-proportioned and with thickness no less than 7cm.

<3>. Save the ultrasonic B image, hang off ultrasonic B probe from the selected position, and change to liver fibrosis scanning model. Hold the fibrosis scanning probe in right hand, bend forefinger to keep probe perpendicularly at the selected position on the skin, lie right elbow on the bed (to avoid the right arm from shaking and moving), and left hand hold the tail of the probe to control the direction. Press the probe slightly on patients' skin to make the pressure indicating strip turn green.

<4>. With subject holding his or her breath slightly, operator observes the liver tissue displayed by ultrasonic-M signal. When the tissue is dark, more homogeneous and laminar distribution, the operators can press down the foot switch, and the fibrosis scanning probe sent out low-frequency shear waves for diagnosing and ultrasonic waves for monitoring, the probe is activated and complete once examination of LSM.

<5>. Ten times of successful detection are performed at the same position. When the inter

quartile range (IQR) value is qualified, the median value of these detections will be considered as the examination result of LSM.

<6>. Save and print the test result.

◆ The operator of FibroTouch must be trained by Hisky and obtain an operating license or certificate.

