◆ A successful and effective test by FibroTouch must meet the following requirements: ultrasonic-A signal does not have intensive and rapid shaking, and does not fluctuate significantly in different depth; ultrasonic-M signal does not have big difference of lightness and displays a laminar distribution pattern in different depth; ultrasonic-E signal presents a routine white-and-black twill diagram.

◆ Each subject will obtain 10 successful acquisitions and the median value of these acquisitions will be considered as the examination result of LSM and FAP. The IQR-to-median ratio of the 10 acquisitions should be ≤ 0.3 (the smaller the IQR value, the reliable the result is). If the result is not reliable, it should be detected again until the result is reliable.

◆ To avoid artificial errors, the instrument needs to be operated by a fixed professional in each site, and all information will be documented in a uniform model and stored in U-disk, keep by a designated personnel.

6. FibroScan Examination

6.1 At the same site as that for FibroTouch, the stiffness of liver is determined via Fibroscan at the same day.

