6.2 Operation procedure

(1) Keep in a supine position, lift up both hands to expose the intercostal gap in the area of right liver lobe of chest, and take a deep breath to make the intercostal gap as large as possible at the time of determination.

(2) Vertically stick the probe smeared with coupling agent to the intercostal gap.

(3) Determination site: Select the intercostal gap at the anterior or middle axillary line between the Rib 8~10 for routine determination, or adjust the determination site until the optimal one according to the real-time audiovisual diagram if the determination fails at the routine site.

(4) Observe the audiovisual diagram displayed in the instrument, and press the emission button for determination when there is a laminar liver image.

(5) Determine effectively for 10 times, and regard the mean of these 10 determinations as the determination result.

7. Liver biopsy

Within 3 months before the FibroTouch examination, puncture the 16G liver biopsy needle into 1.5~2.0cm of liver tissues (≥ 8 complete portal areas), fix with 10% neutral formalin, embed with paraffin wax, make the continuous section for HE, Masson and reticular fiber staining (make the HE staining at every study unit, and send another 6 white films to the central laboratory). Then, three pathologists interpret the films independently according to the standard and modified Chevallier semi-quantitative scoring method in the “Protocol for Prevention and Treatment of Viral Hepatitis (2001)”. The interpretation result of these three pathologists should be verified as well consistent through the Kappa test, and otherwise the specimen of inconsistent interpretation result is sent for central interpretation and evaluation.

(1) The liver fibrosis is staged and scored through the following protocol:

① National Protocol for Prevention and Treatment of Viral Hepatitis (2000): staging of liver fibrosis

② Chevallier System (SSS scoring)

③ Metavir System

④ Ishak System

(2) Evaluation protocol for inflammatory activity level and histological activity index (HAI):

① National Protocol for Prevention and Treatment of Viral Hepatitis (2000): grading of inflammation severity

② Ishak Modified HAI: ____/18 (maximum score)

③ METAVIR System: histological activity score

(IV) Safety Evaluation

1. Clinical Safety Evaluation

The clinical safety is evaluated through the adverse events reported by the patients or observed by the doctors.

2. AE

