◆ By grouping according to the grading result via golden standard, the inter-group comparison is made on the FibroTouch determination results through the variance analysis or Wilcoxon rank-sum test, the correlation between two groups is tested through the Spearman correlation analysis, and the correlation coefficient (r) and 95% CI are calculated for two groups.

◆ By regarding the different grading results of golden standard as the judgment critical point, the curve of receiver operating characteristic (ROC) for elasticity value is constructed. The subjects are grouped by regarding the different determination results of elasticity value as the judgment critical point, the sensitivity/specificity is calculated according to the grading result of golden standard, the ROC curve is plotted through the X-axis of specificity, the Y-axis of sensitivity and the calculated result, and the area under curve and its 95% confidence interval are calculated. The critical value corresponding to whichever is greater for the result of sensitivity and specificity is regarded as the judgment critical point for FibroTouch determination value, and then the corresponding sensitivity, specificity, positive predicted value and negative predicted value are calculated.

Comparison of secondary objective: by statistically assuming the success rate of FibroTouch is non-inferior to that of Fibroscan, the critical value of non-inferiority is 10%; and by statistically assuming the determination result of FibroTouch is equivalent to that of Fibroscan, the critical value of equivalence is 1.5KPa.

In the above analysis, $P < 0.05$ indicates a significant difference.

(VIII) Data Management and Data Traceability

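### The 1.5 kPa equivalence comparison sets a FibroTouch median with a spread limit and repeats against a FibroScan mean with no stated spread limit, so identical devices can differ by rule alone, by an unknown amount and sign

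*Combined protocol and SAP*

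**What the plan says.** Section II (II) lists as a secondary objective "Difference between FibroTouch and FibroScan in the determined values". Section IX (VII) turns this into a test: "by statistically assuming the determination result of FibroTouch is equivalent to that of Fibroscan, the critical value of equivalence is 1.5KPa". It does not say how each device's value is to be formed for that test.

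The values are defined under IX (III):

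- **FibroTouch (item 5).** "Each subject will obtain 10 successful acquisitions and the median value of these acquisitions will be considered as the examination result of LSM"; step <5> agrees. There is a spread condition, "The IQR-to-median ratio of the 10 acquisitions should be ≤ 0.3", and a repeat rule, "If the result is not reliable, it should be detected again until the result is reliable".
- **FibroScan (item 6.2, step 5).** "Determine effectively for 10 times, and regard the mean of these 10 determinations as the determination result". No IQR/median limit and no repeat rule for spread is given. Step 3 allows the site to be changed only if determination fails at the routine site. What makes a determination effective is not defined.

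Item 6.1 has both devices used at the same site on the same day, so the comparison is paired.

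**The concern.** Same-day, same-site pairing is meant to leave the device as the source of any difference. Here two other sources remain.

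1. **Mean against median.** The two coincide on average for symmetric readings. The mean is higher if readings are right-skewed or include high outliers, and lower if they are left-skewed.
2. **The FibroTouch spread limit with repeats.** It selects which sets of 10 count. Whether the retained medians are higher or lower than the rest depends on the shape of the readings.

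The two effects may oppose or reinforce each other. At stake is what the equivalence result means: part of the 1.5 kPa margin can be used up, or a true device difference masked, by the summary rule. A mean is also exposed to a single bad reading in a way that a median of 10 is not, and no stated FibroScan rule would catch one.

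**Working it through.** **The plan's own figures.** The margin is 1.5 kPa. Section V gives 423 cases for sensitivity. An exact one-sided binomial test of 0.61 against 0.55 (alpha 0.05, power 80%) reproduces 423, and 423/0.80 = 528.75, stated as 529. Those numbers size the primary aim; no SD, power or sample size is given for the 1.5 kPa test.

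**Inputs from the documents.** 10 readings per device; median, IQR/median <= 0.3 and repeats for FibroTouch; mean for FibroScan; cut-offs of 7.3, 12.4 and 17.5 kPa in the background, used here only as illustrative stiffness levels; 500 final cases (Section V: "600 qualified cases are included to guarantee 500 final statistical cases").

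**Assumptions.** The shape and spread of readings within an examination, quartiles by linear interpolation, and a repeat treated as a fresh independent set of 10.

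**Step 1: identical devices.** Simulate many sets of 10 from one distribution. FibroScan is the average of the means of all sets. FibroTouch is the average of the medians of sets meeting the limit. The filter part is the average median of all sets minus that of the retained sets. CV is the within-examination coefficient of variation.

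| Assumed readings | Spread | FibroScan minus FibroTouch | Filter part | Total at 17.5 kPa |
|---|---|---|---|---|
| Normal | IQR/median 0.2 | -0.12% | -0.12% | -0.02 kPa |
| Normal | IQR/median 0.3 | -1.05% | -1.05% | -0.18 kPa |
| Normal | CV 30% | -2.8% | -2.8% | -0.50 kPa |
| Log-normal | IQR/median 0.2 | +0.87% | -0.06% | +0.15 kPa |
| Log-normal | IQR/median 0.3 | +1.79% | -0.28% | +0.31 kPa |
| Left-skewed | CV 30% | -8.0% | -4.5% | -1.39 kPa |
| Normal, 10% of readings doubled | CV 10% | +8.8% | +0.4% | +1.53 kPa |
| Shifted exponential | CV 30% | about +11% | about +2% | about +1.9 kPa |

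The last column is the percentage times 17.5, for example 0.0179 x 17.5 = 0.31. The shifted-exponential row is relative to the FibroTouch value. The doubled-readings case gives +0.64 kPa at 7.3 kPa and +1.09 kPa at 12.4 kPa. The filter part takes both signs.

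**Step 2: effect on the test.** Section IX (VII) names no test. Assume two one-sided 5% tests on the mean paired difference, with n = 500 and an assumed SD:

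P(equivalence) = Phi((1.5 - d)/se - 1.645) - Phi((-1.5 - d)/se + 1.645), with se = SD/sqrt(n) and d = FibroScan minus FibroTouch.

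- Identical devices, no rule effect (d = 0): about 1.00 at SD 5 kPa, 0.913 at SD 10.
- Identical devices, average rule effect 0.30 kPa: 0.842 at SD 10.
- Identical devices, average rule effect 1.09 kPa: at SD 5, se = 0.2236 and (1.5 - 1.09)/0.2236 - 1.645 = 0.189, so P = 0.575; at SD 10, P = 0.233.
- FibroTouch truly 1.5 kPa higher, where P should be 0.05, with rule effect +0.30 (d = -1.2): 0.165 at SD 10, 0.381 at SD 5, 0.72 at SD 3.
- FibroTouch truly 1.5 kPa lower, same rule effect (d = +1.8): 0.010 at SD 10, 0.001 at SD 5.

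The rule effect can thus lower power when the devices agree, and can raise or lower the chance of declaring equivalence when they differ by the margin.

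**The case against.** - **Each device under its own rule is a legitimate comparison.** That stands as a possible question. The plan does not say that it is the question intended, and such a result cannot separate device from rule.
- **FibroScan may have a quality criterion.** The word used for its 10 determinations may imply one. This stands in part: no limit is stated, but it cannot be inferred that none is applied in practice.
- **The size is assumption-driven.** This stands. No reading-level data or SD is given, the test is not named, and the protocol does not say whether a repeat is a new full set. The figures show what is possible, not what is expected.
- **Applying the IQR limit to FibroScan in the lead analysis could do more harm than the mild cases.** This stands. If 72% of FibroScan results were kept (the background's effective-detection rate, not tied there to an IQR limit), 0.72 x 500 = 360 pairs remain. Power at d = 0 and SD 10 falls to 77%, against 84% with a 0.30 kPa rule effect. Pairs would be lost non-randomly, and FibroTouch would still be repeated while FibroScan was excluded.

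A reader might infer that the FibroTouch filter always makes FibroScan read lower. It does so for normal and log-normal readings, but the filter part is positive with a few doubled readings at CV 10% and with shifted-exponential readings.

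**Conclusion.** The point holds and is worth fixing, with medium confidence. The two values entering the 1.5 kPa comparison are formed by different rules, and nothing in the plan puts them on a common basis. Size and sign are unknown. For tight readings without outliers the effect is a small part of the margin; with outlying or strongly skewed readings it can reach or exceed 1.5 kPa at 17.5 kPa. All of this rests on assumed reading distributions and, for the decision probabilities, on assumed SDs and an assumed test.

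Three further inferences are not supported. One is that the comparison is biased in a known direction or already invalid: with symmetric, tight readings the effect is essentially zero. The opposite one is that it is harmless unless the true difference lies near the margin: an average offset of 1.09 kPa would cut power for identical devices to about 57% at SD 5. The third is that diagnostic accuracy is affected: the primary FibroTouch-versus-biopsy analysis and its sample size do not use the FibroScan value.

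**What to change.** 1. In IX (III) 6.2, step 5, replace the mean by the median, and record the 10 FibroScan readings, or at least their median, IQR and mean. Do this before data collection: if only the mean is kept, the median cannot be recovered.
2. In the SAP, which IX (VII) says is prepared after the protocol is settled, base the 1.5 kPa comparison on medians from both devices in all pairs.
3. Report two sensitivity analyses: (a) the same comparison restricted to pairs in which both devices meet IQR/median <= 0.3; (b) the comparison with the FibroScan mean, as now written.
4. State that the IQR limit is not used to reclassify FibroScan results in the separate 10% success-rate non-inferiority test.

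**Cost.** A small recording burden and no extra measurement. The lead analysis keeps whatever offset the FibroTouch filter causes. That is about 1% or less for normal or log-normal readings up to IQR/median 0.3. At CV 30% it is about 2% for shifted-exponential, 2.8% for normal and 4.5% for left-skewed readings (0.045 x 17.5 = 0.79 kPa). Analysis (a) examines this: in the simulation model, identical devices under the same median and limit differ by zero on average. Its price is fewer pairs, which is why it does not lead.

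### The rule for choosing the FibroTouch cut-off has no unique usable solution as written, and accuracy at the chosen cut-off is reported uncorrected and without a stated confidence interval

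*Combined protocol and SAP*

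**What the plan says.** Section IX (VII), item 2, builds an ROC curve for the elasticity value at each biopsy threshold. For the curve it plans an interval: "and the area under curve and its 95% confidence interval are calculated". The cut-off is then chosen by this sentence: "The critical value corresponding to whichever is greater for the result of sensitivity and specificity is regarded as the judgment critical point". The text continues "and then the corresponding sensitivity, specificity, positive predicted value and negative predicted value are calculated".

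No sum, product, distance, minimum value or tie rule is given there or elsewhere in the document. A 95% interval is named for the correlation coefficient and the AUC, but not for the four measures at the cut-off. No validation sample or resampling is planned. The opening of section IX (VII) foresees a statistical analysis plan to be discussed with the principal investigator; it does not say that the cut-off rule will be revisited.

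The study goal (section III) is "To determine the diagnostic accuracy, specificity and sensitivity of FibroTouch for liver fibrosis assessment in CHB patients".

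**The concern.** Sensitivity and specificity are the stated goal and the basis of the sample size, and both depend on the cut-off. The Background says that few studies have compared FibroTouch with biopsy, so the cut-offs derived here are a main product of the study. A rule that cannot be applied as worded leaves the analyst to choose a criterion, possibly after seeing the ROC curves.

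The smaller matter is that the patients who select the cut-off also supply the accuracy figures. A criterion that maximises something in the sample tends to overstate it, and without intervals the reader cannot judge the precision.

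**Working it through.** **1. The literal rule.** Call a patient positive when LSM ≥ c. If c is at or below the lowest diseased value, sensitivity = 1. If c is above the highest non-diseased value, specificity = 1. So max(sensitivity, specificity) reaches 1, its ceiling, over a whole range at each end of the scale. This follows from the definitions and needs no model. In simulated studies of 500 under the binormal models of step 4, 12–34% of candidate cut-offs tie at the optimum.

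**2. Do the usable readings agree?** The inputs are the Background's hepatitis C figures for another device: F0–1 5.5 (4.1–7.1), F2 6.6 (4.8–9.6), F3 10.3 (7.6–12.9), F4 30.8 (16.3–48) kPa.

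Assumptions: the ranges are quartiles and LSM is log-normal. Then log-SD = ln(Q3/Q1)/1.349:
- F0–1: ln(7.1/4.1)/1.349 = 0.41
- F2: ln(9.6/4.8)/1.349 = 0.51
- F3: ln(12.9/7.6)/1.349 = 0.39
- F4: ln(48/16.3)/1.349 = 0.80

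Section V asks for at least 100 "cases are required for S0+S1, S2, S3, S4 and liver cirrhosis (compensatory stage) respectively". Pooling the last two as F4 gives weights 1:1:1:2; 1:1:1:1 is the alternative.

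Example at ≥F2, weights 1:1:1:2, c = 7.5 kPa:
- Specificity = Φ(ln(7.5/5.5)/0.41) = 0.78.
- The shares at or above 7.5 kPa are 0.40 (F2), 0.79 (F3) and 0.96 (F4).
- Sensitivity = (0.40 + 0.79 + 2 × 0.96)/4 = 0.78.

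This is the equal-measures cut-off. Maximising the sum instead gives 9.0 kPa with 0.70/0.89.

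| Threshold | Weights | Youden: kPa (sens/spec) | Equal: kPa (sens/spec) | Gap, kPa |
|---|---|---|---|---|
| ≥F2 | 1:1:1:2 | 9.0 (0.70/0.89) | 7.5 (0.78/0.78) | 1.5 |
| ≥F2 | 1:1:1:1 | 8.4 (0.66/0.85) | 7.2 (0.74/0.74) | 1.2 |
| ≥F3 | 1:1:1:2 | 9.9 (0.80/0.86) | 9.3 (0.82/0.82) | 0.6 |
| ≥F3 | 1:1:1:1 | 9.0 (0.79/0.81) | 8.8 (0.80/0.80) | 0.2 |
| ≥F4 | either | 14.6 (0.82/0.92) | 12.8 (0.86/0.86) | 1.8 |

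The closest-to-corner and largest-product rules fall between these two. At ≥F2 (1:1:1:2) they give 8.0 and 8.5 kPa. The largest shift in one measure is in specificity at ≥F2, about 11 points (0.885 − 0.778).

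**3. When the choice does not matter.** With equal-variance normal groups all four rules meet at the midpoint. A curve of that kind through the planning pair of section V (0.61/0.90) gives 0.78/0.78 under every rule. With a diseased-to-non-diseased SD ratio of 2, Youden gives 0.62/0.89 and the equal rule 0.73/0.73. The planning pair is a mean over stages, so this is illustrative.

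**4. Optimism under Youden, N = 500.** Groups of 100/100/100/200. Binormal curves pass through the Background's hepatitis B FibroScan pairs (≥F2 0.66/0.83, ≥F3 0.58/0.95, ≥F4 0.60/0.93), with SD ratios from 1 to 2.5. Optimism is apparent minus true sensitivity plus specificity at the selected cut-off, in points:

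| Threshold | Ratio 1 | 1.5 | 2 | 2.5 | Hepatitis C model |
|---|---|---|---|---|---|
| ≥F2 | 4.0 | 3.8 | 3.4 | 3.1 | 3.0 |
| ≥F3 | 2.6 | 2.7 | 2.5 | 2.3 | 2.3 |
| ≥F4 | 2.6 | 2.7 | 2.5 | 2.2 | 2.0 |

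The largest single component is specificity at ≥F2, about 3 points, because only about 100 patients define it. Under the equal rule the optimism is close to zero (0.4 points or less in the hepatitis C model).

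**5. The missing intervals.** At the planned values, the 95% half-width for specificity at ≥F2 with 100 patients is 1.96 × √(0.90 × 0.10/100) = 5.9 points. For sensitivity at ≥F4 with 200 patients it is 1.96 × √(0.61 × 0.39/200) = 6.8 points.

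**The case against.** The document is a rough English rendering, and nobody would set a cut-off at the extreme of the observed values. On that view the sentence is a poor translation of a largest-sum rule, and a later analysis plan may say so. Most of this is fair: Youden is the likely intention, and the defect is an unnamed criterion, not an impossible analysis. But the word that would settle it is absent, and the later plan is only foreseen.

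The kPa gaps are also fragile. They come from another disease and device, and two of the three shrink when the stage weights change. The log-normal model fits ≥F4 imperfectly: it gives an AUC of about 0.94, against 0.97 in the Background. The two rules differ in sensitivity plus specificity by only 2.7, 0.3 and 1.1 points at ≥F2, ≥F3 and ≥F4 (1:1:1:2), so they mainly trade one measure for the other. This all stands, and the gaps should be read as illustration.

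A reader might set the gaps against the plan's statement that "the critical value of equivalence is 1.5KPa". That limit concerns agreement between FibroTouch and FibroScan readings, not the choice of cut-off, so the comparison does not carry over.

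**Conclusion.** The point holds: the only stated cut-off rule fails if followed, nothing else in the document repairs it, and the study goal depends on it. Confidence is high for that. The size of the consequence is model-dependent: from no difference (equal-variance normal groups) to 1.8 kPa and about 11 points in one measure. No FibroTouch data enter these figures.

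The secondary point is real but modest: about 2–4 points in the sum under Youden, and no stated interval for any of the four measures.

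A reader might infer that optimism could carry the device past a pass mark, since section V says "the lowest clinically acceptable sensitivity and specificity is 0.55" (0.8 for specificity). The documents do not support that: these figures enter the sample-size calculation, and no test against them is planned. Nor does the point touch the AUC, which needs no cut-off. Deriving a cut-off in this study is reasonable, provided it is labelled as derivation. This should be fixed, and it is cheap to fix.

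**What to change.** Replace the cut-off sentence with:

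> For each biopsy threshold the cut-off is the LSM that maximises sensitivity + specificity − 1 (Youden index), a criterion fixed before database lock. Sensitivity, specificity, PPV and NPV at that cut-off are reported with 95% CIs as derivation-sample estimates, with a bootstrap optimism-corrected estimate (cut-off re-selected in each resample) alongside the apparent one.

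Any single named criterion would cure the main defect; Youden is proposed because it is probably what was meant. A Wilson interval shifted by the estimated optimism is enough. In a check of 400 simulated studies it covered the true accuracy at the selected cut-off in 92–96% (Monte Carlo error about 1 point).

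The cost is two sentences and one bootstrap program, with no extra patients or visits. Reported accuracy will be about 1–2 points lower per measure. The bootstrap removes most of the optimism, not all of it.

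### The trial is sized to test sensitivity against 0.55 and specificity against 0.80, but the analysis section contains no such test and no confidence interval for either, so the stated 80% power attaches to no planned analysis.

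*Combined protocol and SAP*

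**What the plan says.** Section V (Anticipated Total Cases) takes its expected accuracy from published FibroScan work: "the mean sensitivity and specificity are 0.61 and 0.90 respectively for different stages". It then sets floors: "the lowest clinically acceptable sensitivity and specificity is 0.55" "and 0.8 respectively, when $\alpha=0.05$ and power=80" per cent. From these it derives "423 cases are required based on sensitivity", raised to 529 because only 80% of determinations are expected to be valid, and "328 cases are required based on specificity", raised to 410 in the same way. Enrolment is at least 600, and these "qualified cases are included to guarantee 500 final statistical cases". At least 100 cases are wanted in each of five groups: S0+S1, S2, S3, S4 and compensated cirrhosis.

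Section IX (VII) 2 plans comparisons of FibroTouch values between histological groups, a Spearman correlation with a 95% interval, and ROC curves with the area under the curve and its 95% interval. A cut-off is then read from the ROC results, "and then the corresponding sensitivity, specificity, positive predicted value and negative predicted value are calculated". The only margins in the analysis section belong to the secondary comparisons with FibroScan: 10% for success rate and 1.5 kPa for measured values. A closing sentence sets P<0.05 as the significance level.

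**The concern.** A sample-size calculation with a null value, an alternative, an alpha and a power describes a test. Here the test appears only in section V. The analysis section gives sensitivity and specificity no null value, test, confidence interval or success rule. It does not say whether both floors must be met, or at which fibrosis threshold.

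Two things are at stake. First, the trial could be completed exactly as planned and still give no formal answer to the question it was sized for, namely whether accuracy exceeds the stated minimum. Second, the accuracy figures it does give would be point estimates at a cut-off chosen on the same subjects. Such estimates tend to be optimistic, and the plan supplies neither an interval nor a correction.

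**Working it through.** **Inputs.** From section V: sensitivity 0.61 against 0.55; specificity 0.90 against 0.80; alpha 0.05 (sidedness not stated); power 80%; 80% valid determinations; 500 final cases; five groups of at least 100.

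**Step 1: reproduce the plan's figures.** For a one-sample exact binomial test, take the smallest critical count r with P(X ≥ r | n, p0) ≤ 0.05, then the smallest n with P(X ≥ r | n, p1) ≥ 0.80.

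- Sensitivity, p0 = 0.55, p1 = 0.61, one-sided: n = 423, r = 250 (250/423 = 59.1%), actual alpha 0.0495, power 80.3%. This is the plan's figure exactly, and 423/0.8 = 528.75, rounded up to 529.
- The same test at one-sided 0.025 needs 538, and the two-sided normal approximation about 533. Neither matches, so the implied test is one-sided at 5%.
- Specificity, p0 = 0.80, p1 = 0.90, one-sided: n = 82 non-diseased, r = 72 (87.8%), actual alpha 0.0458, power 80.6%. The plan's 328 equals 82/0.25, so it reproduces if 25% of subjects are assumed non-diseased. The documents do not state that share. Then 328/0.8 = 410.

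The 80% power is therefore that of a one-sided test against each floor, separately.

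**Step 2: look for that test in the analysis section.**

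| Quantity | Null value or margin | Interval planned | Test planned |
|---|---|---|---|
| Group differences in FibroTouch value | no difference (implied) | no | yes |
| Spearman correlation | none stated | 95% | yes |
| Area under the ROC curve | none | 95% | no |
| Sensitivity, specificity | none | none | none |
| Success rate against FibroScan (secondary) | 10% | none stated | non-inferiority |
| Measured value against FibroScan (secondary) | 1.5 kPa | none stated | equivalence |

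The floors 0.55 and 0.80 do not appear after section V.

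**Step 3: power if the implied test is added.** Assume 500 final cases split as 100 per group, and a true accuracy of 0.61/0.90 at the threshold concerned. Diseased and non-diseased subjects are different people, so at a fixed cut-off the power to pass both tests is the product of the two.

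| Threshold | Diseased / non-diseased | Minimum correct, sensitivity | Power, sensitivity | Minimum correct, specificity | Power, specificity | Power, both |
|---|---|---|---|---|---|---|
| ≥S2 | 400 / 100 | 237 | 77.9% | 87 | 87.6% | 0.779 × 0.876 = 68% |
| ≥S3 | 300 / 200 | 180 | 66.2% | 170 | 99.0% | 0.662 × 0.990 = 66% |
| ≥S4 incl. cirrhosis | 200 / 300 | 123 | 47.3% | 252 | >99.9% | 47% |

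The count of 423 refers to diseased subjects. With equal groups no threshold reaches it, although ≥S2 comes close.

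**The case against.** **The goal is estimation.** Section III speaks of determining accuracy, sensitivity and specificity, and the area under the curve has an interval. This carries some weight: a pure estimation study would be legitimate. But section V sets minimum acceptable values with an alpha and a power, and even an estimation study needs intervals for sensitivity and specificity, which are absent.

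**The P<0.05 sentence covers it.** It does not, because the analysis section gives no null value for either measure.

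**A later SAP will supply the test.** Section IX (VII) says an analysis plan is to be prepared after the protocol is settled. It could close the gap, but no such further plan is in the documents, and the rule has to be fixed before results are seen.

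**Stronger readings.** A reader might infer that FibroTouch will be declared acceptable whenever its point estimates clear the floors. Under that rule a true sensitivity of exactly 0.55 would pass 50.6% of the time at n = 423, and a true specificity of exactly 0.80 would pass 52.2% of the time at n = 82. The documents state no such rule, or any acceptance rule, so these are not error rates of the plan.

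A reader might also infer that the ROC-chosen cut-off will move away from 0.61/0.90 and cost specificity. That would need a model for the ROC curve and a reading of an unclear cut-off rule. Section V also describes 0.61 and 0.90 as means over several stages, so they are not the operating point of any one threshold. The documents do not support a figure for such a shift.

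**Conclusion.** The point holds. The hypothesis that determined the sample size is not tested, and sensitivity and specificity are reported without intervals at a cut-off selected from the same data. The stated 80% power belongs to no planned analysis, and the plan cannot formally conclude that its minimum accuracy is met.

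The finding rests on the text of two sections and on the exact match at 423. It needs no modelling assumption. The match for 328 does need an unstated 25% non-diseased share, but the finding does not depend on it.

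The power figures for the repaired analysis assume about 100 subjects per group, a true accuracy of 0.61/0.90 at the chosen threshold, and a fixed cut-off. The direction of the cut-off selection bias (optimistic) is clear; its size cannot be derived from the documents.

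**What to change.** In section IX (VII) 2:

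1. Report confidence intervals for sensitivity and specificity at every fibrosis threshold.
2. Add a primary test: FibroTouch meets its minimum accuracy only if the one-sided 95% lower limit for sensitivity exceeds 0.55 and that for specificity exceeds 0.80. State that the limits are one-sided, which matches the calculation behind 423. Because both are required, neither needs a multiplicity adjustment.
3. Name one primary fibrosis threshold in advance. With equal groups, ≥S2 has the most diseased subjects and the highest sensitivity power. Results at other thresholds can be descriptive.
4. Deal with cut-off selection. Either fix the cut-off before the analysis, or use an optimism-corrected bootstrap or cross-validation in which each selected cut-off is evaluated on subjects not used to select it. Do not choose the cut-off in-sample to reach specificity 0.90 and then test specificity on the same subjects. That test would pass automatically: 90 of 100 already has a one-sided exact lower limit of 0.836, whatever the device.
5. Restate the power in section V for the chosen threshold, for each floor and for both together.

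**Cost.** This adds a short passage to the analysis section and some programming for the resampling. The sponsor commits to a pass/fail rule that the device may not meet. At ≥S2 with 400 and 100 subjects, sensitivity power is slightly below 80% (about 78%) and power for both floors is about 68%. If 80% is wanted for the joint criterion, the sample size must be revisited.
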